7.5 Prior and Concomitant Medications

All prior and concomitant medications will be coded using WHO-DDE (Format C English, March 2016) on the FAS subjects and summarized separately. Each prior or concomitant medication will be classified using the ATC classification system and mapped to a WHO-DDE preferred drug name. A subject will be counted at most once for each prior or concomitant medication, respectively, even if the subject took the same prior or concomitant medication on multiple occasions.

7.6 Treatment Compliance

Treatment compliance will be calculated as described in Section 4.5.3. Compliance rate for FAS subjects will be summarized by study period (Day 1 - Month 1, Month 1 - Month 2, and Month 2 - Month 3).

7.7 Treatment Exposure

Treatment exposure to the study medication is measured by days on treatment as derived in Section 4.1.6. Subjects in the Safety Population will be tabulated by duration category (0-30, 31-60, 61-90, and > 90 days).

7.8 **Pregnancy During the Course of the Study**

Urine pregnancy test will be performed on all women of childbearing potential at the Screening, Baseline (Day 1), Month 3 or early termination visits. For subjects who become pregnant during the course of the study, their positive testing results will be provided in a listing.

8 EFFICACY ANALYSES

Unless specified otherwise, all efficacy analyses will be performed on the analysis eye of the FAS population.

For each efficacy measure listed in Section 4.3, correlation coefficients, scores and change-frombaseline scores will be summarized descriptively by analysis visit. There will be no formal hypothesis testing because this is a single-arm, open-label study.

8.1 Analyses of Primary Efficacy Endpoints

The primary efficacy endpoints are:

- Correlation between the change from baseline in VMR measured with FVA system at Month 3 and the change from baseline in the CFS at Month 3.
- Correlation between the change from baseline in variance of OSI measured with double pass aberrometer at Month 3 and the change from baseline in the CFS at Month 3.

8.1.1 Primary Analyses of the Primary Endpoints

Spearman's coefficient of correlation and its 95% confidence interval will be calculated at Month 3 between the change from baseline of CFS and, respectively, the change from baseline of VRM and the change from baseline of variance of OSI.

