## 4.3 Benefit risk balance

The patients participating in the study will benefit from IKERVIS®, a product marketed for the treatment of severe keratitis in adult patients with dry eye disease, which has not improved despite treatment with tear substitutes. Based on inclusion criteria patients will have visual function deficiencies in addition to severe keratitis and it is expected to be improved with IKERVIS® (main objective of the study). Patients will benefit from a close follow-up by the investigators (every month) which is not the case in the usual clinical practice. The risks related to the participation of the study are the adverse events listed on the SmPC, the potential risk of allergy to fluorescein, anaesthetic eye drops or artificial tears and the potential irritation related to the Schirmer test examination.

In light of the points listed above the benefit risk balance is considered favourable.

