# 5.0 STUDY OBJECTIVES AND ENDPOINTS

## 5.1 Objectives

# 5.1.1 **Primary Objective(s)**

The primary objective of the study is to assess the effect on the quality of vision of IKERVIS® (1mg/ml ciclosporin) eye drops administered once daily in adult dry eye disease (DED) patients with severe keratitis following 3 months of treatment, assessed by Functional Visual Acuity (FVA) and Objective Scatter Index (OSI), and to estimate the correlation of the change of Visual Maintenance Ratio (VMR) measured with FVA system and variance of OSI, separately with the expected Corneal fluorescein staining (CFS) improvement.

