## **12.0 STATISTICAL METHODS**

## **12.1** Statistical Analysis

Descriptive statistics (mean, standard deviation, 95% confidence interval for mean, minimum, median, maximum, and number of observations and missing cases) will be used for quantitative variables, and frequencies and percentages will be used for categorical variables. For the variables recorded for both eyes, the descriptions will be given separately for the analysis eye and for the fellow eye, when considered relevant.

All the efficacy analysis will be performed on the analysis eye, which is defined as the eligible eye that fulfils all the criteria listed under the inclusion criteria #4. If both eyes are eligible, the eye with the highest baseline CFS score will be chosen. If both eyes have the same CFS score, the eye with the lowest VMR will be chosen. If VMR values are the same for both eyes, the right eye will be chosen.

A Statistical Analysis Plan will be written and signed before starting the analysis of the study data. This document will present all the analyses to be performed, and detail some points of the protocol.

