2.1.1 Primary Objective

The primary objective of the study is to assess the effect on the quality of vision of IKERVIS® (1 mg/mL ciclosporin) eye drops administered once daily in adult dry eye disease (DED) patients with severe keratitis following 3 months of treatment, assessed by Functional Visual Acuity (FVA) and Objective Scatter Index (OSI), and to estimate the correlation of the change of Visual Maintenance Ratio (VMR) measured with FVA system and variance of OSI, separately, with the expected Corneal fluorescein staining (CFS) improvement.

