During the Baseline Visit, patients will be instructed to instill one drop of study medication (IKERVIS® 1mg/mL) once daily in each eye at bedtime and will be scheduled for three additional study visits, Month 1 (Day 28 ± 3), Month 2 (Day 56 ± 3), and Month 3 (Day 84 ± 7). In addition to the study medication, patients will also be allowed to use unpreserved artificial tears provided by the Sponsor, up to eight instillations per day in each eye, to alleviate their dry eye symptoms. Patients must be instructed not to use artificial tears within 30 minutes before or after use of the study medication and within two hours before a scheduled study visit. All concomitant medications will be recorded on the case report form (eCRF). A change in the use of the study treatments (or any topical eye drops other than the study medication or the Sponsor provided unpreserved artificial tears or topical medications allowed during the study) will be considered a protocol violation. In this phase IV clinical trial, the Month 3 Visit assessments will be used to assess the efficacy (quality of vision and other parameters) and safety of IKERVIS® in DED patients with severe keratitis.

The study flowchart is illustrated in Figure 1.

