6 GENERAL CONSIDERATIONS

Statistical analyses will be performed based on this SAP by the Biometry Unit of Euraxi, a contract research organization (CRO) based in Joué Les Tours, France.

Unless specified otherwise, all efficacy analyses will be performed using data from the analysis eye of FAS subjects, and all safety variables will be analyzed separately for both the analysis eyes and the fellow eyes on the Safety population.

Continuous variables will be summarized using descriptive statistics such as number of observations (n), mean, standard deviation, median, minimum, and maximum. Categorical variables will be tabulated using frequency (n) and percent (%).

All statistical testing will be conducted at a significance level of 0.05 (two-sided) unless specified otherwise. No statistical testing will be conducted for safety measures.

All data manipulations, descriptive summaries, and statistical testing will be performed using SAS Version 9.4 or later.

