8.2 Analyses of Secondary Efficacy Endpoints

8.2.1 Analyses of Continuous Secondary Efficacy Endpoints

The following continuous variables will be summarized using descriptive statistics such as number of observations (n), mean, standard deviation, coefficient of variation, median, minimum, and maximum by analysis visit.

- CFS scores assessed at each visit with the Modified Oxford Scale and change from baseline at Months 1, 2 and 3.
- FVA parameters (VMR, LogMAR FVA, starting visual acuity, and minimal and maximal VAs) assessed at each visit and their change from baseline at Months 1, 2 and 3.
- OSI and its variance assessed at each visit and their change from baseline at Months 1, 2 and 3.
- Root mean square (RMS) of higher order aberrations (total, coma-like, spherical like) measured with Hartmann-Schack aberrometer at each visit and their change from baseline at Month 3.
- Tear break up time (TBUT) assessed at each visit and change from baseline at Months 1, 2 and 3.
- VAS scores (photophobia, blurred vision) assessed at each visit and their change from baseline at Months 1, 2 and 3.
- Artificial tear usage assessed at each visit and change from baseline at Months 1, 2 and 3.

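### Both primary endpoints are rank correlations and cannot show whether vision changed; the Month 3 mean changes need to be tied to the objective with 95% CIs, and the LogMAR CV and the SAP's VMR formula are wrong as written

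*SAP*

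**What the plan says.** The objective has two parts. Protocol 5.1.1 opens: "The primary objective of the study is to assess the effect on the quality of vision of IKERVIS", to be judged by functional visual acuity (FVA) and OSI after 3 months. SAP 2.1.1 repeats this and continues "and to estimate the correlation of the change of Visual Maintenance Ratio (VMR) measured with FVA system and variance of OSI, separately", with the expected CFS improvement. Protocol 4.3 gives the first part weight, saying of visual function that "it is expected to be improved with IKERVIS® (main objective of the study").

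Both primary endpoints are correlations (Protocol 5.2.1, SAP 2.2.1). SAP 8.1.1 states: "Spearman's coefficient of correlation and its 95% confidence interval will be calculated at Month 3". The mixed model in SAP 8.1.2 is a sensitivity analysis, and Appendix B extracts from it only the slope on CFS change and its p-value.

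Changes in the FVA parameters, OSI and its variance are secondary endpoints (SAP 2.2.2.1). For these SAP 8.2.1 lists n, "mean, standard deviation, coefficient of variation, median, minimum, and maximum by analysis visit". The general rule in SAP 6 is: "Continuous variables will be summarized using descriptive statistics such as number of observations (n), mean, standard deviation, median, minimum, and maximum". Protocol 12.1 has a longer list: "Descriptive statistics (mean, standard deviation, 95% confidence interval for mean, minimum, median, maximum, and number of observations and missing cases").

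Protocol 12.4 wants a CV for every criterion, to inform a further study. SAP 10.2 converts the acuities to LogMAR before any analysis.

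VMR is defined in three ways. Protocol 9.3.4.1 divides FVA by starting acuity. Protocol Appendix A-IV uses distances from the lowest LogMAR score. SAP 4.3.1 divides LogMAR FVA by starting LogMAR acuity and calls an increase an improvement.

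**The concern.** A result labelled primary should bear on the primary objective. Here the primary statistics would be identical whether vision improved, stayed flat or worsened on average. A reader looking for the effect on vision must choose among several FVA parameters, two OSI parameters and three visits, with no sentence saying which summary answers the question and no interval named for any of them.

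The CV and VMR rules matter separately. The CV is meant to guide a later study, but on LogMAR it depends largely on where the scale's zero happens to lie. VMR enters one of the two primary correlations and an entry criterion, so a formula that runs the wrong way would affect more than a descriptive table.

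**Working it through.** The documents give no sample-size calculation (SAP 3.3) and no SD for any change score, so there is no planned figure to reproduce. Intervals are therefore in SD units, and assumed values are marked.

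**1. Shift invariance.** Spearman's rho uses ranks. Adding a constant to every patient's vision change leaves the ranks, and so rho, unchanged. One simulated data set with n = 17, re-centred three times:

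| Mean VMR change | rho with CFS change | 95% CI for the mean |
|---|---|---|
| -0.10 | -0.471 | -0.127 to -0.073 |
| 0 | -0.471 | -0.027 to 0.027 |
| +0.10 | -0.471 | 0.073 to 0.127 |

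**2. Width of the missing interval.** The half-width is t(0.975, n-1)/√n SDs: 0.373 at n = 30, the planned number of completers; 0.514 at n = 17, the number enrolled (SAP 3.1); 0.554 at n = 15; and 0.635 at n = 12.

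**3. CV on LogMAR levels.** The device range is 150/100 to 20/200 (Protocol Appendix A-IV). By the SAP 10.2 formula this is -log10(1.5) = -0.18 to -log10(0.1) = 1.00, so zero (decimal acuity 1.0) lies inside it. For comparison, Protocol 7.2 equates LogMAR 1.0 with 35 letters and Appendix A-III gives 0.02 per letter, so letters = 35 + (1.0 - L)/0.02 = 85 - 50L. With an assumed SD of 0.15 LogMAR (7.5 letters):

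| Assumed mean LogMAR | CV in LogMAR | Same data in letters |
|---|---|---|
| 0.20 | 0.15/0.20 = 75% | 7.5/75 = 10.0% |
| 0.10 | 0.15/0.10 = 150% | 7.5/80 = 9.4% |
| 0.02 | 0.15/0.02 = 750% | 7.5/84 = 8.9% |
| -0.05 | 0.15/(-0.05) = -300% | 7.5/87.5 = 8.6% |

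At a mean of zero the LogMAR CV is undefined.

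**4. CV of change scores, n = 17.** The 95% sampling range of mean/SD comes from the noncentral t with 16 df and is inverted to a CV. The chance of a wrong sign is Φ(-ratio × √17).
- Assumed true mean/SD 0.25: wrong sign 15% of the time; the range of mean/SD, -0.236 to 0.810, spans zero.
- 0.5: wrong sign 2%; CV range 89% to about 4000%.
- 1: CV range 56% to 199%.
- 2: CV range 31% to 74%.

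**5. VMR.** Take starting acuity 0.8 (LogMAR 0.0969), with FVA improving from 0.5 (0.3010) to 0.7 (0.1549):
- Protocol 9.3.4.1: 0.5/0.8 = 0.625 to 0.7/0.8 = 0.875, change +0.25.
- Appendix A-IV, assuming the lowest score is 1.00: 0.6990/0.9031 = 0.774 to 0.8451/0.9031 = 0.936, change +0.16.
- SAP 4.3.1: 0.3010/0.0969 = 3.106 to 0.1549/0.0969 = 1.598, change -1.51.

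The SAP ratio is undefined at starting acuity 1.0, where the denominator is zero. Above 1.0 the denominator is negative and the direction reverses. Below 1.0, a ratio under 0.95, as entry requires, would need average acuity over the test to be better than starting acuity.

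**The case against.** The strongest reply is that the effect part is already analysed. SAP 8 and 8.2.1 summarise change by visit with n, mean and SD. SAP 8.1.2 tabulates VMR and OSI-variance change by CFS-change category, and SAP 8.2.4 charts means with error bars. SAP 3.1 adds that "the Month 3 Visit assessments will be used to assess the efficacy (quality of vision and other parameters") and safety. The study is exploratory, with no multiplicity control and no formal hypothesis testing (SAP 6.4, 8), so the primary label decides little. This stands: what is missing is a named link and an interval, not the data or the summaries.

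A reader might infer that no 95% CI is planned, or that the SAP removed one without saying so. The documents do not support either reading. Protocol 12.1 specifies the interval, both SAP lists are open-ended, and the SAP says it applies to protocol version 3.0, while the protocol supplied is version 4.0. A reader can also compute the interval from n, mean and SD.

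It is also fair that the CV is required by the protocol, is printed beside the mean and SD, and is less of a problem for levels of OSI and its variance. The figures of 750% and -300% rest on an assumed SD and chosen means.

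On VMR, SAP 4.3.1 says FVA parameters come from the measurement system, and the conversion list in SAP 10.2 omits VMR. That suggests, without proving, that VMR is exported by the device and the SAP formula never applied. In that case only the text is wrong.

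**Conclusion.** The point holds in a limited form. Neither primary endpoint can estimate a change in vision; this is a property of rank correlation and needs no assumption. The effect part of the objective is described only by secondary summaries that no sentence ties to it, and the SAP does not name the interval the protocol specifies.

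It would go too far to say that the effect part is unanswered, or to read 0.51 against 0.37 SD as the cost of the omission. That gap comes from having 17 patients rather than 30 and is the same whether or not the interval is printed.

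Two rules are wrong as written. The LogMAR CV can be undefined, negative or arbitrarily large; how far it would go here depends on means and SDs the documents do not give. For change scores the CV is unstable when mean/SD is small and usable at about 1 or more. The SAP's VMR ratio falls as FVA improves whenever starting acuity is unchanged and worse than 1.0. This contradicts its own direction of improvement and both protocol definitions, and it does not fit the entry criterion.

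No version of these estimates can be attributed to the drug. There is no control arm, and in the pivotal trial described in Protocol 4.1.3 the vehicle group's CFS also improved, by 1.48 grades against 1.81.

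**What to change.** 1. In SAP 8.1, name the Month 3 mean changes from baseline, each with a 95% CI, as the estimates for the effect part. Include LogMAR FVA and OSI, the measures closest to that part's wording, together with VMR and variance of OSI. Word them as change during treatment in a single arm, and record in SAP 10 that they were specified after enrolment. State the missing-data rule for each, since the carry-forward rule in SAP 6.2.1 names VMR and variance of OSI but not LogMAR FVA or OSI. The primary endpoints do not change.
2. Add the Protocol 12.1 interval for means to SAP 6 and 8.2.1.
3. Drop the CV for LogMAR variables. For change scores report mean, SD and CI instead. Record both in SAP 10 as a departure from Protocol 12.4.
4. Before any VMR analysis, reconcile Protocol 9.3.4.1, Protocol Appendix A-IV and SAP 4.3.1, and state which definition was computed or that the device exported the value.

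The cost is SAP text and a CI column in existing tables; no new data are needed. The intervals will be wide, about 0.51 SD either side if all 17 patients contribute and more if fewer do, and the designation comes after open-label enrolment.

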8.2 Analyses of Secondary Efficacy Endpoints

8.2.1 Analyses of Continuous Secondary Efficacy Endpoints

The following continuous variables will be summarized using descriptive statistics such as number of observations (n), mean, standard deviation, coefficient of variation, median, minimum, and maximum by analysis visit.

- CFS scores assessed at each visit with the Modified Oxford Scale and change from baseline at Months 1, 2 and 3.
- FVA parameters (VMR, LogMAR FVA, starting visual acuity, and minimal and maximal VAs) assessed at each visit and their change from baseline at Months 1, 2 and 3.
- OSI and its variance assessed at each visit and their change from baseline at Months 1, 2 and 3.
- Root mean square (RMS) of higher order aberrations (total, coma-like, spherical like) measured with Hartmann-Schack aberrometer at each visit and their change from baseline at Month 3.
- Tear break up time (TBUT) assessed at each visit and change from baseline at Months 1, 2 and 3.
- VAS scores (photophobia, blurred vision) assessed at each visit and their change from baseline at Months 1, 2 and 3.
- Artificial tear usage assessed at each visit and change from baseline at Months 1, 2 and 3.

8.2.2 Analyses of Categorical Secondary Efficacy Endpoints

The following categorical variables will be tabulated using frequency (n) and percent (%).

- CFS scores assessed at each visit will also be summarized categorically.
- Shift from baseline in CFS scores at Months 1, 2, and 3.
- Patient global evaluation of efficacy at Month 3/early termination visit.
- Investigator global evaluation of efficacy at Month 3/early termination visit.

8.2.3 Correlation Analyses

8.2.3.1 Correlation Analyses for Data Collected from the Same Visits

Spearman's coefficients of correlation and its 95% confidence interval will be calculated at each follow-up visit between the change from baseline of the following pairs of variables (Month 1 vs. Month 1, Month 2 vs. Month 2, and Month 3 or Month 3, respectively):

- Change from baseline in CFS vs. the change from baseline of following variables, respectively:
 - FVA parameters
 - > VMR
 - ➢ LogMAR FVA
 - Starting visual acuity (LogMAR scale)
 - Minimal visual acuity (LogMAR scale)
 - Maximal visual acuity (LogMAR scale)
 - OSI parameters
 - > OSI
 - Variance of OSI
 - o VAS symptom scores
 - Blurred vision
 - Photophobia
 - o TBUT
 - Schirmer's test
 - o HOA RMS
 - Visual acuity
 - BCDVA (logMAR)
 - ➢ UDVA (logMAR)
- Change from baseline in **FVA (logMAR)** vs. the change from baseline of following variables, respectively:
 - o OSI parameters
 - > OSI
 - Variance of OSI
 - VAS symptom scores
 - Blurred vision
 - Photophobia
 - o TBUT
 - Schirmer's test
 - HOA RMS
 - o Visual acuity

- ➢ BCDVA (logMAR)
- ➢ UDVA (logMAR)
- Change from baseline in **OSI** vs. the change from baseline of following FVA parameters, respectively:
 - VMR
 - Starting visual acuity (LogMAR scale)
 - Minimal visual acuity (LogMAR scale)
 - Maximal visual acuity (LogMAR scale)
- Change from baseline in **variance of OSI** vs. the change from baseline of following FVA parameters, respectively:
 - o VMR
 - Starting visual acuity (LogMAR scale)
 - Minimal visual acuity (LogMAR scale)
 - Maximal visual acuity (LogMAR scale)

8.2.3.2 Correlation Analyses for Lagged Data

Spearman's coefficients of correlation and its 95% confidence interval will be calculated for the following pairs of variables:

- 1) CFS vs. VMR
 - Change from baseline in CFS at Month 1 vs. change from baseline in VMR at Month 2
 - Change from baseline in CFS at Month 1 vs. change from baseline in VMR at Month 3
 - Change from baseline in CFS at Month 2 vs. change from baseline in VMR at Month 3
- 2) CFS vs. LogMAR FVA
 - Change from baseline in CFS at Month 1 vs. change from baseline in LogMAR FVA at Month 2
 - Change from baseline in CFS at Month 1 vs. change from baseline in LogMAR FVA at Month 3
 - Change from baseline in CFS at Month 2 vs. change from baseline in LogMAR FVA at Month 3
- 3) CFS vs. OSI
 - Change from baseline in CFS at Month 1 vs. change from baseline in OSI at Month 2
 - Change from baseline in CFS at Month 1 vs. change from baseline in OSI at Month 3
 - Change from baseline in CFS at Month 2 vs. change from baseline in OSI at Month 3

- *4) CFS vs. Variance of OSI*
 - Change from baseline in CFS at Month 1 vs. change from baseline in variance of OSI at Month 2
 - Change from baseline in CFS at Month 1 vs. change from baseline in variance of OSI at Month 3
 - Change from baseline in CFS at Month 2 vs. change from baseline in variance of OSI at Month 3
- 5) CFS vs. VAS Symptom Score of Photophobia
 - Change from baseline in CFS at Month 1 vs. change from baseline in VAS symptom score of photophobia at Month 2
 - Change from baseline in CFS at Month 1 vs. change from baseline in VAS symptom score of photophobia at Month 3
 - Change from baseline in CFS at Month 2 vs. change from baseline in VAS symptom score of photophobia at Month 3
- 6) CFS vs. VAS Symptom Score of Blurred Vision
 - Change from baseline in CFS at Month 1 vs. change from baseline in VAS symptom score of blurred vision at Month 2
 - Change from baseline in CFS at Month 1 vs. change from baseline in VAS symptom score of blurred vision at Month 3
 - Change from baseline in CFS at Month 2 vs. change from baseline in VAS symptom score of blurred vision at Month 3

